Title of protocol: The Effect of Preventive Drug Therapy on Central Pain in Patients with Spinal Cord Lesions

Date: February 1, 2023

Version: 8

Primary investigator: [name], PhD

IRB-number: 0012-19-LOE

Objectives:

To examine whether preventative pregabalin treatment prevents the development of neuropathic pain following spinal cord lesions (SCL).

Setting:

The Spinal Rehabilitation Department, Loewenstein Rehabilitation Medical Center, Raanana, Israel.

Study design:

Non-randomized, interventional study.

Methods:

Participants: 50 SCL patients. Inclusion criteria: age 18 and above; up to 3 months following traumatic or non-traumatic SCL; ability to give informed consent and cooperate. Exclusion criteria: pregnancy; neurological or other medical conditions that may interfere with sensation; neuropathic-like pain before recruitment (described as painful sensation of electric current, burning, numbness, tingling, pricking, or squeezing); being treated with pregabalin; blood creatinine levels >1.2 ; creatinine clearance <60 ; sensitivity to lactose. Informed consents will be obtained from the patients who conformed with the inclusion/exclusion criteria. Participants who do not cooperate, wish to withdraw, develop pregabalin side effects, or are transferred to another hospital, where treatment of the pain is changed, will be removed from the study.

Treatment: Participants will be sequentially allocated to 2 groups. One group will include 2/3 of the patients and will receive preventive pregabalin for 12 weeks; the second (control) group will include the other 1/3 of the patients and will not receive preventative analgesics. The dose of the preventive pregabalin will be $75\text{mg} \times 1$ (once daily) for the first 3 days, and $75\text{mg} \times 2$, for the rest of the treatment period, followed by a week of gradual dosage decrease until the preventive treatment stops.

In case of pain without neuropathic characteristics, treatment will be with paracetamol or NSAIDs, according to the decision of the attending physician in the Spinal Rehabilitation Department. If neuropathic pain, as described above, is diagnosed, the pregabalin dose may be increased up 600 mg/day in total. If the pain persists, the drug therapy may change according to the policy of the department.

Follow-up: Demographic and clinical data will be collected from the patients' medical records.

Before starting the preventive treatment, and at 6 and 12 weeks from start (and at the respective periods for the control group), patients will complete the following questionnaires: background data (only before start), 0-10 visual analogue scale for pain (VAS), the Pain Catastrophizing Scale, the Depression Anxiety and Stress Scale (DASS), the Body Vigilance Scale (BVS), and the DSM-V for post-traumatic stress disorder. At those times and at 3 and 9 weeks from start, patients will be interviewed about the development of pain. If pain is reported at the interviews or between them, patients will be asked to complete the McGill Pain Questionnaire to help characterize it.

A physician in the Spinal Rehabilitation Department will interview patients in the pregabalin group about one month after the start of treatment to identify suicidal thoughts, which are possible side effect.

At 6 and 12 months after being included in the study, participants will be interviewed about the development of pain to investigate the long-term effect of the treatment; if needed, they will complete the McGill Pain Questionnaire.

In case of discharge from the Spinal Rehabilitation Department before 12 weeks from inclusion in the study, treatment and follow-up will continue. Adverse events will be reported according to the Israeli Ministry of Health regulations.

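### The only definition of the pain is a list of six qualities with no link to the lesion, so new pain unrelated to the cord lesion can be counted

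*Protocol*

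**What the plan says.** The title is "The Effect of Preventive Drug Therapy on Central Pain in Patients with Spinal Cord Lesions". The Objectives paragraph is worded differently: it asks whether preventive pregabalin stops neuropathic pain from developing after a cord lesion.

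The pain is defined once, in the exclusion criteria under Methods, Participants. Neuropathic-like pain before recruitment is "described as painful sensation of electric current, burning, numbness, tingling, pricking, or squeezing". The Treatment paragraph applies the same description to pain during the study: "If neuropathic pain, as described above, is diagnosed".

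The Follow-up paragraphs say how new pain is found. At baseline and at 3, 6, 9 and 12 weeks, "patients will be interviewed about the development of pain". If pain is reported, "patients will be asked to complete the McGill Pain Questionnaire to help characterize it". The interview, with the McGill questionnaire if needed, is repeated at 6 and 12 months.

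The protocol does not mention where the pain is, the neurological level, or how pain from the cord is told apart from pain of a nerve root or peripheral nerve. One criterion comes near the subject, the exclusion of "neurological or other medical conditions that may interfere with sensation", and it applies at entry.

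**The concern.** Title and objective both attribute the pain to the cord lesion. The definition tests only what the pain feels like. A patient with a thoracic lesion who develops painful tingling in a hand some weeks after inclusion meets it, although the hand lies above the lesion. The entry exclusion does not help, because this pain did not exist at entry.

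If such pains are counted, two errors are possible. If pregabalin does not affect them, they add the same background to both groups and shrink a real effect on lesion-related pain. If pregabalin suppresses them, they can produce a difference between groups while lesion-related pain is unchanged.

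The point belongs in the protocol because it concerns what is asked at the interview. An analysis plan written later cannot reliably classify pains by level if their site was not recorded at the time, least of all for interviews after discharge.

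**Working it through.** **Where the text could supply a link to the lesion**

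| Place in the protocol | What it adds | Link to the lesion |
|---|---|---|
| Exclusion criteria, pain description | Six qualities | None |
| Treatment, on-study diagnosis | Refers back to the six qualities | None stated |
| Follow-up interviews | Development of pain | No site mentioned |
| McGill questionnaire | Helps to describe the pain | No rule for using site |
| Exclusion of sensory conditions | Removes existing conditions | Entry only |

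No row separates pain due to the lesion from other pain with the same qualities.

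**Illustration of size**

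From the protocol: "Participants: 50 SCL patients", with 2/3 on pregabalin and 1/3 control. 50 × 2/3 = 33.3 and 50 × 1/3 = 16.7, so about 33 and 17. The protocol states no event rate, effect size or power, so there is no figure to reproduce. All risks below are assumptions.

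Let p be the risk of central pain and q the risk of unrelated pain with the listed qualities, taken as independent. The counted risk is 1 − (1 − p)(1 − q).

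*Dilution.* Central pain is 40% in controls and 20% on pregabalin, with q equal in both groups. At q = 10%, controls are 1 − 0.60 × 0.90 = 46% and pregabalin is 1 − 0.80 × 0.90 = 28%. Power is for a two-sided 5% comparison of two proportions (pooled standard error under no difference, unpooled under the alternative).

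| q | Control | Pregabalin | Difference (points) | Risk ratio | Power |
|---|---|---|---|---|---|
| 0% | 40% | 20% | 20 | 0.50 | 33% |
| 10% | 46% | 28% | 18 | 0.61 | 25% |
| 20% | 52% | 36% | 16 | 0.69 | 19% |
| 30% | 58% | 44% | 14 | 0.76 | 15% |

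With control central risk anywhere from 30% to 50%, still halved by the drug, power is 25% to 43% at q = 0 and 13% to 27% at q = 20%.

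*Apparent effect.* Central pain is equal in both groups, and pregabalin halves the unrelated pain. At p = 30% and q = 20%, controls are 1 − 0.70 × 0.80 = 44% and pregabalin is 1 − 0.70 × 0.90 = 37%, a ratio of 0.84. Over p = 30% to 50% and q = 10% to 30%, the apparent difference runs from 2.5 points (55.0% vs 52.5%, ratio 0.95) to 10.5 points (51.0% vs 40.5%, ratio 0.79).

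A more extreme case has unrelated pain at 20% vs 5% and central pain at 30% in both groups. Controls are 1 − 0.70 × 0.80 = 44.0% and pregabalin is 1 − 0.70 × 0.95 = 33.5%, a ratio of 0.76. The standard error is √(0.44 × 0.56/17 + 0.335 × 0.665/33) = 14.6 points, so the difference is 10.5/14.6 = 0.7 standard errors. About 11% of such trials would reach significance.

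**The case against.** Four objections carry weight.

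- **The six qualities are not a stated endpoint.** They explain an exclusion criterion and recur in a sentence about treatment. No sentence says which pains the analysis counts. This stands. A reader might infer that the protocol fixes any one of the six qualities as the trial's event, and it does not say that. It does offer this as its only definition, so unrelated pain *can* be counted, and no text prevents it.
- **Diagnosis implies judgement.** A clinician in a spinal rehabilitation department may well recognise hand pain from nerve compression as such. The interview and questionnaire forms are not reproduced, so site may already be noted. This also stands in part. But the sentence refers the diagnosis back to the six qualities, and no rule makes the judgement the same for every patient and both groups.
- **The objective is broader than the title.** Root pain arising with the lesion can fall within neuropathic pain after a cord lesion. So a reader who concludes that the result could not answer the objective goes too far. Much of the mismatch is with the word central in the title. Pain above the level fits neither wording.
- **Location is an imperfect test.** It is tempting to make below-level pain the sole event. That would drop at-level pain, which may come from the cord, and would still admit leg pain from a compressed nerve in a patient with a thoracic lesion. The documents do not support such a rule, and it is not proposed here.

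**Conclusion.** The gap is real and worth closing: the protocol's only definition of the pain does not tie it to the cord lesion, although title and objective do. It leaves room for unrelated new pain to enter the comparison. It does not show that such pain will be counted, or how often.

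The size cannot be taken from the document. Under the assumed rates above, dilution is the more plausible harm, with a true ratio of 0.50 read as 0.61 to 0.76. A reader might also infer that the trial is likely to claim prevention of central pain falsely. The figures do not support that. It needs a drug effect confined to unrelated pain, and even the extreme case rarely reaches significance with 33 and 17 patients. Nor is the definition the main limit on precision, since power is only 33% in the illustration before any unrelated pain is added.

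The results rest on independence of the two kinds of pain, on a split of 33 and 17 with no dropout, and on assumed risks throughout.

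**What to change.** 1. At each existing pain interview and McGill completion, in both groups and by the same written rule, record the site of each pain as above, at or below the patient's neurological level. State which assessment of the level is the reference.
2. Do not count above-level pain as lesion-related neuropathic pain.
3. Report at-level and below-level pain with the listed qualities separately and combined. Keep the descriptor-only count as a sensitivity result.
4. Limit any statement about central pain to the below-level result, and say that location is an imperfect marker of central origin.
5. Align the wording of the title and the objective.

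The cost is one item per pain report, with no added visit, and a somewhat smaller event count. It assumes that the neurological level is among the clinical data taken from the medical records, which the protocol does not spell out. The change concerns only what is recorded and counted and leaves the treatment rules as they are.

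### Removing patients from the study, not only from the drug, when pregabalin side effects occur loses pain outcomes almost only in the pregabalin group

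*Protocol*

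**What the plan says.** The study is described as a "Non-randomized, interventional study" in "50 SCL patients". Two thirds are allocated to preventive pregabalin and one third to no preventive analgesic. The single stated objective is whether pregabalin prevents neuropathic pain after a spinal cord lesion.

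The Participants paragraph (Methods) lists four grounds for removal. The first two are non-cooperation and a wish to withdraw. The other two apply to those who "develop pregabalin side effects, or are transferred to another hospital, where treatment of the pain is changed, will be removed from the study". No grade or seriousness of side effect is specified.

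The Treatment paragraph adds: "If neuropathic pain, as described above, is diagnosed, the pregabalin dose may be increased up 600 mg/day in total".

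The Follow-up section sets the pain interviews. Besides the questionnaire visits before start and at 6 and 12 weeks, it says: "At those times and at 3 and 9 weeks from start, patients will be interviewed about the development of pain". At 6 and 12 months, "participants will be interviewed about the development of pain to investigate the long-term effect of the treatment". It also schedules, in the pregabalin group only, a physician interview at about one month to look for one named side effect.

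The only situation in which follow-up is expressly continued is early discharge: "In case of discharge from the Spinal Rehabilitation Department before 12 weeks from inclusion in the study, treatment and follow-up will continue".

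**The concern.** The removal rule is triggered by an event after allocation that depends on which group the patient is in. A control can develop a pregabalin side effect only if given pregabalin later, after neuropathic pain has been diagnosed. The side-effect ground therefore takes patients out of one arm and leaves the other almost untouched.

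The pregabalin patients who remain are those who tolerated the drug, and they would be compared with an unselected control group. If tolerating the drug is related to the risk of neuropathic pain, the selection can look like a preventive effect or can hide one. The 6- and 12-month interviews, meant to show the long-term effect, are lost in the same patients.

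Transfer with changed pain treatment is a separate matter. It can occur in either group, but it may be related to pain, which is the outcome.

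**Working it through.** **Does the text mean that interviews stop?** Three points, side by side:

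- The rule removes the patient from the study and does not mention stopping the drug as a separate step.
- Where follow-up is meant to go on after a change in the patient's situation (early discharge), the protocol says so.
- No corresponding sentence covers removed patients.

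The plain reading is that interviews stop, although the protocol does not state it in so many words.

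**What is lost.** Six interviews follow the start of treatment: 3, 6, 9 and 12 weeks, and 6 and 12 months. A patient removed before week 3 misses all six. One removed between weeks 3 and 6 misses five.

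**Inputs.** From the protocol: 50 patients and a 2:1 split. This gives 50 × 2/3 = 33.3, about 33 on pregabalin, and about 17 controls. The protocol gives no rate of side effects, removal or pain. The following are therefore assumptions:

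- p = 0.40, the true pain incidence in both groups (no drug effect)
- f = share of the pregabalin group whose outcome is lost: 10%, 20% or 30% (about 3, 7 or 10 of 33, leaving 30, 26 or 23)
- k = pain risk in those patients relative to the group average: 0.5, 1, 1.5 or 2
- no removals among controls, unless stated

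**Formula.** Incidence among those retained = (p − f·k·p) / (1 − f). The bias is this value minus p.

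Example with f = 0.20 and k = 1.5: (0.40 − 0.20 × 1.5 × 0.40) / 0.80 = 0.28 / 0.80 = 0.350, a false benefit of 5.0 points.

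| k | f = 10% | f = 20% | f = 30% | Bias (points) |
|---|---|---|---|---|
| 0.5 | 42.2% | 45.0% | 48.6% | false harm 2.2, 5.0, 8.6 |
| 1 | 40.0% | 40.0% | 40.0% | 0 |
| 1.5 | 37.8% | 35.0% | 31.4% | false benefit 2.2, 5.0, 8.6 |
| 2 | 35.6% | 30.0% | 22.9% | false benefit 4.4, 10.0, 17.1 |

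With p varied from 0.30 to 0.50 and k from 0.5 to 1.5, the bias runs from a false benefit of 10.7 points to a false harm of 10.7 points.

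**Removals in both groups.** With k = 2, 20% lost from pregabalin gives 30.0% and 10% lost from control gives 35.6%. The bias falls from 10.0 to 5.6 points. With equal loss and equal k it is 0. It is the imbalance that does the damage.

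**Bounds without an assumption on k.** If 7 of 33 pregabalin outcomes are missing, best-case and worst-case incidence differ by 7/33 = 0.212, or 21 points.

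**The case against.** The strongest reply has four parts.

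1. *The dose-increase route does not lose the incident outcome.* The increase follows a diagnosis of neuropathic pain, so the development of pain should already be on record. Removal after that loses the later course, and incidence is biased only if recorded outcomes are discarded. The protocol does not say that they are, and how recorded data are handled may properly be left to the analysis plan. This stands. The main concern rests on patients removed before any pain has been recorded.

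2. *The sizes are assumed, and the upper end is extreme.* At 40% incidence, k = 2 means that 80% of removed patients would develop neuropathic pain. The 17.1-point figure combines this with 30% loss and no control removals. This also stands, and that corner should be read as an outer limit. Against a standard error of √(0.24/33 + 0.24/17) = 14.6 points for the risk difference, biases of 2.2 to 5.0 points are about 0.15 to 0.34 of one standard error. Bias, however, does not average out as random error does, and the loss it comes from is avoidable.

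3. *The study is not randomized, so no randomized comparison is at stake.* This does not answer the point. Selection after allocation would distort even perfectly comparable groups, and baseline adjustment would not reliably remove it.

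4. *An analysis plan may deal with missing outcomes.* It can choose an analysis set or an imputation method. It cannot supply interviews that the protocol's own rule prevents.

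**Conclusion.** The concern holds. Followed as written, the side-effect rule ends outcome collection for a reason that exists almost only in the pregabalin group, and it acts on the study's sole stated objective. The statement about one-sided loss applies to the side-effect ground only; the other grounds can arise in both groups.

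Neither the direction nor the size of the bias can be determined from the protocol. At an assumed 40% incidence and with 10% to 30% of pregabalin outcomes lost, it ranges from 8.6 points of false harm (k = 0.5), through zero, to 8.6 points of false benefit (k = 1.5), and to 17.1 points in the most extreme case shown. The conclusion depends on reading removal from the study as the end of the interviews. If that was not intended, the sentence still needs correcting. Because the lost interviews cannot be recovered later, the rule should be changed in the protocol and not left to the analysis.

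**What to change.** Separate stopping study drug from leaving the study. A possible wording:

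> Participants who stop pregabalin, whose pain treatment is changed, or who are transferred remain in the study and continue the planned pain interviews (3, 6, 9 and 12 weeks; 6 and 12 months), unless they withdraw consent or cannot be assessed, for example because they do not cooperate. Outcomes recorded before any removal are kept.

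Decisions on stopping or changing drugs are not affected.

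Two further points could go in the protocol or the analysis plan: compare the groups as allocated, with an analysis restricted to those who tolerated the drug as secondary; and report removals by group and reason.

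**Cost.** One amended sentence, probably with ethics review since the protocol is under IRB oversight, and continued contact with a few patients. If 7 patients were removed, this is at most 7 × 6 = 42 interviews, all of which the schedule already foresees for them. Follow-up after discharge is already planned, though only for patients still on treatment, so it is a partial precedent. There are two drawbacks. Patients in other hospitals are harder to reach, and the effect in the allocated groups may be diluted by patients who stopped the drug; the secondary analysis would show the result in those who tolerated it.

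### Apart from one interview for suicidal thoughts in the pregabalin group, no scheduled contact is described as asking about side effects, although side effects lead to removal

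*Protocol*

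**What the plan says.** The Follow-up section sets the content of the scheduled contacts. Questionnaires on pain, catastrophizing, mood, body vigilance and post-traumatic stress are completed at baseline and at weeks 6 and 12. The interviews are described as follows: "At those times and at 3 and 9 weeks from start, patients will be interviewed about the development of pain". The McGill questionnaire is added if pain is reported. At 6 and 12 months, "participants will be interviewed about the development of pain to investigate the long-term effect of the treatment".

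One contact is aimed at safety: a department physician will "interview patients in the pregabalin group about one month after the start of treatment to identify suicidal thoughts, which are possible side effect".

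Four other statements bear on harm:

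- Removal (Methods, Participants): "Participants who do not cooperate, wish to withdraw, develop pregabalin side effects, or are transferred to another hospital", in the last case where pain treatment is changed there, leave the study.
- Data source (Methods, Follow-up): "Demographic and clinical data will be collected from the patients' medical records".
- Discharge (Follow-up): "In case of discharge from the Spinal Rehabilitation Department before 12 weeks from inclusion in the study, treatment and follow-up will continue".
- Reporting (Follow-up): "Adverse events will be reported according to the Israeli Ministry of Health regulations".

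**The concern.** A rule that decides who stays in the study needs a defined way of finding the event that triggers it. Here the event is a pregabalin side effect, and for everything except suicidal thoughts the protocol names no occasion on which patients are asked about it.

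Two things are at stake. The first is the harm count. The exclusion criteria rule out patients who already have neuropathic-like pain, so the drug is given to people who may never have developed it, and a reader of the results will weigh pain prevented against harm caused. A side-effect rate gathered unsystematically, with no comparable count in controls, supports that judgement poorly. The second is the efficacy comparison. Removal for pregabalin side effects falls mainly on the treated group, so the way side effects are noticed can influence which treated patients remain to be compared.

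**Working it through.** No figure in the protocol needs reproducing: it states no side-effect rate, detection rate or safety target. The check sets the statements side by side.

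**Step 1. What each contact is described as covering (Follow-up).**

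| Contact | Groups | Described content | Side-effect enquiry named? |
|---|---|---|---|
| Week 3 | both | pain interview | no |
| About 1 month | pregabalin only | physician interview for suicidal thoughts | one event only |
| Week 6 | both | pain interview, questionnaires including the DASS | no |
| Week 9 | both | pain interview | no |
| Week 12 | both | pain interview, questionnaires including the DASS | no |
| 6 and 12 months | both | pain interview | no |

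By count, 0 of the 4 on-treatment interviews are described as asking about side effects. One separate contact asks about a single side effect, in one group.

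**Step 2. Timing.** Treatment lasts 12 weeks and the safety interview is at about week 4. That leaves about 12 − 4 = 8 weeks of treatment with no named safety enquiry of any kind. The Treatment paragraph allows the dose to be raised if neuropathic pain is diagnosed, and this could happen after that interview.

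**Step 3. Whether the other provisions fill the gap.**

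- The adverse-event sentence governs what is done with an event once known. It does not say how events are found.
- Medical records can capture events, but they are named as a source of demographic and clinical data, without mention of side effects. The protocol does not say which records cover a patient after discharge.
- The DASS is given to both groups at baseline and weeks 6 and 12. It bears on mood only, is not presented as a safety measure and is not linked to the removal rule.

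**Step 4. Patients concerned.** 2/3 × 50 ≈ 33 treated; 50 − 33 = 17 controls.

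**Step 5. Whether the under-count can be sized.** Write p for the true proportion with a side effect and d for the fraction detected. Then:

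- recorded events ≈ 33 × p × d
- share missed = 1 − d
- observed difference between groups = p(treated) × d(treated) − p(control) × d(control)

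The protocol supplies no p and no d. With d free between 0 and 1, the share missed can be anything from 0 to 100%, and any chosen d simply returns the assumption. The last line still shows a direction. If the true rates were equal, the observed difference would be p × [d(treated) − d(control)], which is zero only when detection is equal. For suicidal thoughts the protocol makes detection unequal by design, because only the pregabalin group is interviewed about them.

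**The case against.** The strongest reply is that silence is not exclusion. This is a very short protocol. Saying that an interview concerns pain gives its purpose and does not forbid other questions, and side-effect forms may sit in case report forms or a safety procedure that is not shown. No two statements contradict each other: there is a removal rule, a reporting rule and one targeted safety interview. The only stated objective is prevention of neuropathic pain, and no side-effect rate is promised.

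Much of this limits what can be claimed. A reader might infer that side effects come to light only if patients volunteer them. The documents do not support that: the one-month interview actively looks for one side effect, and medical records are a data source. A reader might also infer that a discharged patient with a side effect stays on the drug while an inpatient with the same symptom is removed. That too goes beyond the text. The protocol does not describe outpatient record-keeping, does not restrict the physician interview to inpatients, and speaks of removal from the study, which is not necessarily the same as stopping the drug.

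One warning also stands. The removal rule has no severity threshold, so feeding a symptom checklist straight into it could remove more treated patients and add to selective loss.

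The reply does not dispose of the point. What patients are asked at visits belongs in the protocol, so an unseen statistical analysis plan would not settle it, and the protocol refers to no separate safety procedure. Even with efficacy as the sole objective, the protocol itself makes side effects decide who remains in the study.

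**Conclusion.** The point holds in a limited form. As described, 0 of 4 on-treatment interviews cover side effects. The single active enquiry concerns one event, at about one month, in the pregabalin group only. Other harms are therefore likely to be under-ascertained, and what is actively sought differs between the groups.

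That under-ascertainment is likely is a judgement from the described contacts, not something the document states, and its size cannot be derived. The conclusion assumes that the contacts are carried out as described and that no separate side-effect form is in use. If such a form exists, citing it in the protocol would largely answer the point. The weakness is one of design, cheaply improved, and not an internal contradiction.

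**What to change.** At baseline and at the existing week 3, 6, 9 and 12 contacts, in both groups and irrespective of discharge, add one open question on new symptoms since the last contact and a short fixed list of expected side effects. Record onset date, severity and any change to the study drug. Report rates by group from this record. The baseline entry separates symptoms already present from new ones, and the control count gives the treated rate something to be read against.

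Keep the form separate from the removal rule. An entry of a minor symptom should not by itself take a patient out of the study. The investigators should reconcile how the existing rule is applied with what the form records, and state this in the protocol. The change alters no dose and sets no new clinical rule.

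The cost is a short form at contacts already planned. The downside is that more minor symptoms will be recorded and the side-effect rate will probably look less favourable.

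### Suicidal thoughts are asked about directly only once, about a month into a planned 13-week pregabalin course whose dose can be raised at any time

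*Protocol*

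**What the plan says.** **Direct check.** The Follow-up section of the Protocol has a department physician who "will interview patients in the pregabalin group about one month after the start of treatment to identify suicidal thoughts", and describes such thoughts as a possible side effect. This is the only contact given that purpose.

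**Exposure.** Under Methods, Treatment, the pregabalin group "will receive preventive pregabalin for 12 weeks", "followed by a week of gradual dosage decrease until the preventive treatment stops". After the first three days the preventive dose is 75 mg twice daily, that is 150 mg/day.

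**Dose increase.** The same section adds: "If neuropathic pain, as described above, is diagnosed, the pregabalin dose may be increased up 600 mg/day in total". It sets no earliest or latest date for an increase and no end date for the higher dose.

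**Other contacts.** The Follow-up section states: "At those times and at 3 and 9 weeks from start, patients will be interviewed about the development of pain"; the times meant are baseline and weeks 6 and 12. A further pain questionnaire applies "If pain is reported at the interviews or between them". The DASS and a post-traumatic stress measure are completed at baseline and weeks 6 and 12. Treatment and follow-up go on after an early discharge. Adverse events are reported under national regulations, and there are pain interviews at 6 and 12 months.

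**Removal rule.** Methods, Participants, lists among those to be removed: "Participants who do not cooperate, wish to withdraw, develop pregabalin side effects".

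**The concern.** The protocol treats this hazard as serious enough for a physician to ask about it face to face, and then stops asking while most of the planned exposure is still to come. An increase made before the one-month interview is followed by that check. An increase made after it is not followed by any named question. Patients who stay on 150 mg/day are not asked again either.

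The other provisions do not do the same job. The DASS is not assigned to detecting suicidal thoughts, and no action is attached to a score. The pain interviews are about pain. Adverse event reporting and the removal rule take effect only once someone knows of the event. With the schedule followed as written, thoughts that begin after the first month may go unnoticed unless the patient volunteers them or a contact meant for something else picks them up. The removal rule would then not be triggered, and the patient could remain on the drug. The stake is patient safety.

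**Working it through.** The protocol states no figure on this point, so there is none to reproduce. The check measures how much planned exposure follows the single interview, and what repeating the question would change.

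**Inputs**
- Treatment period: 12 weeks = 84 days (Methods, Treatment).
- Taper: 1 week, giving 84 + 7 = 91 days (Methods, Treatment).
- Interview: about one month (Follow-up). Assumption: day 28 to day 31.
- Later contacts: weeks 6, 9 and 12 = days 42, 63 and 84 (Follow-up).
- Pregabalin group: two thirds of 50, about 33 patients (Methods).

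**Share of planned days after the interview** = (T − m)/T, where T is planned exposure in days and m is the interview day.

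| | m = 28 | m = 30 | m = 31 |
|---|---|---|---|
| T = 84 (no taper) | 56/84 = 66.7% | 54/84 = 64.3% | 53/84 = 63.1% |
| T = 91 (with taper) | 63/91 = 69.2% | 61/91 = 67.0% | 60/91 = 65.9% |

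The range is 63% to 69%, or 53 to 63 days.

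Weighting days by preventive dose hardly changes this. Without taper, the total is 3 × 75 + 81 × 150 = 12,375 mg. The part after the interview is 56 × 150 = 8,400 mg (67.9%) for day 28, or 53 × 150 = 7,950 mg (64.2%) for day 31.

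**Size of a permitted increase:** 600/150 = 4 times the preventive dose.

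**Intervals after the one-month interview if the question is repeated at weeks 6, 9 and 12**
- Interview to week 6: 42 − 31 = 11 to 42 − 28 = 14 days.
- Week 6 to week 9: 63 − 42 = 21 days.
- Week 9 to week 12: 84 − 63 = 21 days.
- Week 12 to end of taper: 91 − 84 = 7 days.

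The longest is 21 days, against 53 to 63 days now. The first 28 to 31 days, before the interview, are unchanged.

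**Beyond the planned course.** The next contact after week 12 is at 6 months. Taking 6 months as 26 weeks and inclusion as the start of treatment (both assumptions), the gap is 26 − 12 = 14 weeks, or 98 days. The 21-day figure therefore does not apply to a patient kept on an increased dose after week 12.

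**The case against.** The strongest reply is that this is a preference about frequency. The protocol names the hazard, assigns a physician, targets the treated group and sets a time; nothing is misstated or contradictory. Any single check leaves time after it, and the document gives no reason to think that later exposure is more dangerous. Later coverage is also not empty. There are interviews at weeks 6, 9 and 12 and a depression scale at weeks 6 and 12, and a dose increase implies clinical contact because neuropathic pain must first be diagnosed. The consent pages are not in the available text, so patients may have been told to report such thoughts.

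Much of this stands as a limit on the claim. Three stronger readings are tempting, and the documents support none of them:
- **That about two thirds of the risk goes unmonitored.** The 63% to 69% counts days. The protocol does not say when the risk arises.
- **That a fourfold dose means a higher risk of suicidal thoughts.** The protocol gives no dose relation, and the point does not need one.
- **That nothing is in place after month one.** Indirect coverage exists; what is missing is a direct question.

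The reply does not remove the core point. The protocol added a physician interview although the DASS was already in the schedule, so the DASS was evidently not meant to serve in its place. It gives no reason why one answer at about a month should serve for the rest of the course, or after an increase that has not yet been made. The contact at which neuropathic pain is diagnosed comes before the increase and is directed at pain. Because the protocol itself fixes this schedule, it is not a detail left to a statistical analysis plan.

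**Conclusion.** The point holds as a safety-monitoring gap that is cheap to close. One direct check is scheduled, and 53 to 63 planned exposure days follow it (63% to 69%), for about 33 patients planned for preventive pregabalin. The range rests on reading one month as 28 to 31 days and on whether the taper is counted. How many patients would have a late dose increase, or how many events would be missed, cannot be estimated from the protocol.

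A reader might infer that the trial's comparison of pain between groups is compromised. It is not: the point concerns the care of treated patients and leaves the efficacy comparison unaffected.

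**What to change.** Keep the one-month physician interview and add the following to the Follow-up section:

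- Put a direct question about suicidal thoughts to pregabalin-treated patients at the existing week 6, 9 and 12 contacts, including after discharge.
- Ask it at the first contact after any dose increase.
- For patients still on pregabalin after week 12, ask it also at the 6- and 12-month interviews. A longer gap remains for them, so the question after a dose increase matters most here.
- Record the current pregabalin dose with each answer.
- Refer any positive answer promptly to the department physician.

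The cost is protocol wording and a few minutes per contact, with no added scheduled visits. The downsides are repeated sensitive questioning and the need for a clear referral route. The latter matters because the protocol does not say who conducts the pain interviews or how they are done after discharge, so whoever does them must be able to ask the question and act on the answer.
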